2.2. Endpoints

Primary Endpoint

- Electronic LogMAR VA under HLLC and LLHC in the 2 testing treatments: AO1D, SCR.

Secondary Endpoint

- Quick Contrast Sensitivity Function under the 2 testing treatments: AO1D, SCR

Other Observation

- Tear Film Interferometry under the 2 testing treatments: AO1D, SCR.

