2.3. Hypotheses

Primary Hypotheses

HLLC and LLHC electronic logMAR Visual Acuity of ACUVUE OASYS® Brand Contact Lenses 1-Day with HydraLuxe™ Technology (AO1D) will be non-inferior to that of best corrected spherocylindrical refraction with trial frame (SCR). A non-inferiority margin of 0.05 (2 and half letters) is assumed.

Secondary Hypotheses

The area under log of the contrast sensitivity function will not be statistically different for ACUVUE OASYS® Brand Contact Lenses 1-Day with HydraLuxe™ Technology compared to best corrected spherocylindrical refraction.

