14.2. Sample Size Justification

There will be one testing site: VRC [REDACTED] A total of approximately 45 eligible subjects will be enrolled into the study at this site. At least 42 subjects will complete this study. The sample size to complete the study is based on the primary hypothesis selected based on the results of a prior Repeatability & Reproducibility (R&R) study regarding ETDRS visual acuity test. The R & R study is a post-hoc analysis of two studies CR-1619 and CR-1622.

Using the POWER procedure in SAS 9.4, below is the summary of sample size required based on the different assumptions of the true difference in electronic LogMAR visual acuity. The sample size was calculated for the non-inferiority tests with at least 90% of statistical power and 2-sided type I error of 0.05. The intraclass correlation was assumed to be 0.5.

Assuming the true difference in electronic LogMAR visual acuity is between 0 (no difference) to 0.02 (one letter), it requires 24 to 63 independent eyes to demonstrate non-inferiority.

- Electronic LogMAR visual acuity

Difference (Test-Control)	Estimated Standard Deviation	# of eyes needed	Power
0.00	0.08	24	0.9
0.02	0.08	63	0.9

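### Section 14.2 gives 90% power for a single non-inferiority test, but the primary hypothesis covers both HLLC and LLHC; if both must pass, power at a true difference of 0.02 is below 90%

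*Combined protocol and SAP*

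**What the plan says.** Section 2.2 defines the primary endpoint as "Electronic LogMAR VA under HLLC and LLHC in the 2 testing treatments: AO1D, SCR". Section 2.3 then hypothesises that "HLLC and LLHC electronic logMAR Visual Acuity of ACUVUE OASYS® Brand Contact Lenses 1-Day with HydraLuxe™ Technology (AO1D) will be non-inferior to that of" trial-frame spherocylindrical refraction, and adds: "A non-inferiority margin of 0.05 (2 and half letters) is assumed".

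Section 14.2 ties the number of completers to the primary hypothesis and says: "The sample size was calculated for the non-inferiority tests with at least 90% of statistical power and 2-sided type I error of 0.05". It also says "The intraclass correlation was assumed to be 0.5", without saying whether this is between eyes or between test conditions. For a true difference of 0 to 0.02 it concludes that "it requires 24 to 63 independent eyes to demonstrate non-inferiority". The table has one endpoint line, one SD (0.08) and one power (0.9) for each assumed difference. HLLC and LLHC are not mentioned there, and neither is joint power.

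Section 14.5 declares non-inferiority when the upper limit of a 95% confidence interval is below 0.05. It does not say whether both conditions have to meet this. Section 14.4 promises a simulation-based multiplicity adjustment and does not name the family of comparisons.

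**The concern.** HLLC and LLHC acuity are measured separately at each treatment visit (steps 2.11 and 3.11), so there are two non-inferiority tests. If the hypothesis stands only when both pass, its power is the probability of two successes, which cannot exceed the power of either test and is lower unless the two estimates are perfectly correlated. Section 14.2 makes no allowance for this.

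The 90% also has to be the power of the test that will be run. Section 14.5 uses a 95% interval, which for non-inferiority is a one-sided 0.025 test. If the tabulated eye counts come from a looser test, the per-chart power is itself overstated, and the joint power built on it is overstated further.

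At stake is what a reader takes from 14.2: the chance that the trial establishes its primary hypothesis if the lens is truly one letter worse (0.02) on both charts.

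**Working it through.** **Inputs.** Margin 0.05 (2.3); SD 0.08, true difference 0 or 0.02, ICC 0.5, 42 completers (14.2); 95% interval (14.5). Assumed: SD and true difference are the same on both charts, and the correlation r between the two charts' estimates is 0 to 0.8. The documents give no value for r.

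**1. Reproduce the plan's eye counts.** Use a paired t-test of the difference against the margin, with noncentrality (0.05 − d) / (0.08/√n) and n − 1 degrees of freedom. The SD of the difference is 0.08. If the table's 0.08 is instead a per-measurement SD with correlation 0.5 between conditions, the result is the same: 0.08 × √(2 × (1 − 0.5)) = 0.08.

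| One-sided alpha | Eyes at d = 0 | Eyes at d = 0.02 |
|---|---|---|
| 0.05 | 24 | 63 |
| 0.025 (two-sided 0.05) | 29 | 77 |
| Stated in 14.2 | 24 | 63 |

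The stated counts match one-sided 0.05 exactly. They do not match the two-sided 0.05 that 14.2 names.

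**2. Per-chart power of 63 eyes at d = 0.02.** The noncentrality is 0.03 / (0.08/√63) = 2.98. Power is 90.3% at one-sided 0.05 and 83.4% at one-sided 0.025.

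**3. Joint power from the stated 90%.** Treat the two test statistics as bivariate normal, each with success probability 0.90, so P(both) = Φ₂(z₀.₉₀, z₀.₉₀; r). This gives 0.810 at r = 0 (0.90 × 0.90), 0.832 at r = 0.5 and 0.856 at r = 0.8.

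**4. From 42 completers to eyes.** Two eyes each gives 84. If the ICC of 0.5 is between eyes, the design effect is 1 + 0.5 = 1.5, and 84/1.5 = 56 effective eyes. If all eyes counted as independent, there would be 84.

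**5. Power under the 14.5 rule (one-sided 0.025) at d = 0.02.**

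| Basis | Per chart | Both, r = 0 | Both, r = 0.5 | Both, r = 0.8 |
|---|---|---|---|---|
| 63 independent eyes | 83.4% | 69.6% | 73.5% | 77.1% |
| 56 effective eyes | 78.7% | 62.0% | 67.0% | 71.4% |
| 84 independent eyes | 92.5% | 85.5% | 87.1% | 89.0% |

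**6. Smaller true differences, same rule.** At d = 0 on both charts, joint power with 56 effective eyes is 99.2% to 99.3%, and with 84 eyes it is higher. At d = 0.01 on both, 56 effective eyes give 92% to 93%. The shortfall is therefore at the 0.02 end of the planning range.

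**The case against.** The strongest objection is that the requirement for both charts to pass is inferred. Section 14.5 gives one rule and no such condition. Section 14.4 promises a multiplicity adjustment, which a both-must-pass rule would not need for this pair. Section 2.3 has a plural heading, and 14.2 speaks of tests in the plural, so a per-test reading of the 90% is available. This stands: the documents do not state the decision rule, and if each chart supported its own claim the joint figures would not apply. Even so, a conjunction is the natural reading of 2.3, and nothing says that one chart alone is enough. On the per-test reading, 63 eyes still do not give 90% under the 95% interval. With 42 completers, the per-chart figure passes 90% only in the case where all 84 eyes are independent.

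Second, r = 0 is the least plausible end of the range, because the same eyes read both charts at the same visit. That is fair, and the upper end deserves more weight; at r = 0.8 every joint figure in step 5 is still below 90%.

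Third, the shortfall needs a true difference of 0.02 on both charts. That is also fair, but 0.02 is the plan's own planning value and the one that produces the 63 eyes.

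A reader might also infer that a split result, one chart passing and the other failing, is about twice as likely as the plan implies. The figures do not support this. With 90% per test, P(exactly one passes) = 2 × (0.90 − joint), which is 18% at r = 0 but only 9% at r = 0.8. The chance of at least one miss is 14% to 19% against 10%, or 1.4 to 1.9 times, and that includes missing on both.

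**Conclusion.** The point holds in this form. Section 14.2 gives a single-test power for a hypothesis that covers two conditions. If both must pass, power at a true difference of 0.02 is below 90%: 81% to 86% with the stated 90% taken at face value, and 70% to 77% for 63 independent eyes under the 95% interval rule. For the planned 42 completers it is 62% to 71% if the ICC is between eyes, rising to 85% to 89% if all 84 eyes are independent.

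These figures rest on an assumed r of 0 to 0.8, a common SD of 0.08 and difference of 0.02 on both charts, and the both-must-pass reading.

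Two stronger conclusions are tempting. One is that the trial is too small and must enrol more. The documents do not support that: at a true difference of 0 joint power is about 99% or more, and the role of the ICC is not defined well enough to fix one figure. The other is that the stated 90% can simply be relabelled as per-chart power. It cannot, because 63 eyes give 83% per chart under the rule in 14.5. The analysis itself is not invalidated; the stated power is not that of the stated hypothesis.

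**What to change.** In 14.5, state that both HLLC and LLHC must meet the 0.05 margin for the primary hypothesis to be established.

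In 14.2, replace the single 90% with per-chart power for 42 completers, recomputed at one-sided 0.025 to match the 95% interval, and say what the ICC of 0.5 refers to so that the conversion from eyes to subjects can be followed. Add the joint HLLC-and-LLHC power over a stated correlation range, for example 0 to 0.8, and quote the joint figure as the power of the primary hypothesis.

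Do not add subjects. The cost is a few sentences and a less favourable stated power.

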14.3. Analysis Populations

The analysis population includes all per-protocol population subjects (see below).

Safety Population:

All subjects who were administered any test article excluding subjects who drop out prior to administering any test article. At least one observation should be recorded.

Per-Protocol Population:

All subjects who have successfully completed all visits and did not substantially deviate from the protocol as determined by the trial cohort review committee prior to database hard lock (Per-Protocol Population). Justification of excluding subjects with protocol deviations in the per-protocol population set will be documented in a memo to file.

Intent-to-Treat (ITT) Population:

All randomized subjects regardless of actual treatment and subsequent withdrawal from study or deviation from protocol. At least one observation should be recorded.

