5.2. Masking

This study is single masked. Masking will be used to reduce potential bias. Subjects will be *unaware* of the identity of the investigational product. Contact lenses in the study will be over-labeled to reduce subject exposure to test product brand.

Under normal circumstances, the mask should not be broken until all subjects have completed the study and the database is finalized. Otherwise, the mask should be broken only if specific emergency treatment/course of action would be dictated by knowing the treatment status of the subject. In such cases, the Investigator may, in an emergency, contact the medical monitor. In the event the mask is broken, the Sponsor must be informed as soon as possible. The date, time, and reason for the unmasking must be documented in the subject record. The Investigator is also advised not to reveal the study treatment assignment to the clinical site or Sponsor personnel.

Subjects who have had their treatment assignment unmasked are expected to return for all remaining scheduled evaluations. Subjects who are discontinued during the enrolment period will be replaced. Once enrolment is completed, no further replacements will be allowed.

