2.8	Subjective Lens Fit Assessment (if applicable)	
The lens fit will be judged to be either acceptable or unacceptable by the investigator based on centration, movement and other fitting characteristics.
 
An unacceptable fit is deemed by one of the following criteria:
 
 • limbal exposure at primary gaze or with extreme eye movement; • edge lift; • excessive movement in primary and up gaze; or • insufficient movement in all three of the following conditions: primary gaze, up gaze, and Josephson push up. 
Note: if lens fit is unacceptable subject will be discontinued from the study.
	 
2.9	Over refraction	Adjust the contact lens or trial frame lens power if the subject's best sphere over-refraction is not plano. Will allow +/-0.25 in the over refraction for -6.00 to -9.00.	
2.10	Lens Power Modification (if applicable)	
For each study lens power modification, repeat steps 2.5 - 2.9
 
Up to three power modifications are allowed.
	
2.11	Distance electronic LogMAR Visual Acuity	
Perform monocular distance Electronic LogMAR visual acuity test at a 4-meter distance OD and OS under the following conditions:
 
 1. bright illumination (e.g., >400 lux), high luminance with low contrast charts (HLLC) 2. dim illumination (e.g., <2.5 lux), low luminance (using neutral density filter), with high contrast charts (LLHC); 	M&S Work Aid 

2.12	qCSF	Perform monocular distance contrast sensitivity test with qCSF. Contrast sensitivity will be tested within the spatial frequency range of 1.5 to 18 cpd for the qCSF method. Area Under the Log CSF (AULCSF) and CSF Acuity will also be collected.	qCSF Work aid
2.13	TFI	Collect images	TFI Work aid
2.14	Lens Removal	Discard lenses after use	
2.15	Slit Lamp (if applicable)	Efron Slit Lamp Classification Scale will be used to grade the findings. Adverse events shall be documented and followed for significant slit lamp findings. If the clearance of the fluorescein needs to be expedited, preservative-free rewetting drops may be instilled.	Workaid: Efron Grading Scale Guideline
2.16	Exit VA	Record the exit distance Snellen visual acuity OD, OS, OU with habitual condition.	████████
2.17		Schedule subject to return in 1-3 days	

VISIT 3

Subjects must not wear contact lenses on the day of this visit

Visit #3 – Treatment #2 (1-3 days): SCR Electronic LogMAR Visual Acuity, QCSF			
Step	Descriptor	Details	████████ Appendix

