8.2. Withdrawal/Discontinuation from the Study

A subject will be withdrawn from the study for any of the following reasons:

- Subject death during the study period
- Subject withdrawal of consent
- Subject not compliant to protocol
- Subject lost to follow-up
- Subject no longer meets eligibility criteria (e.g., the subject becomes pregnant)
- Subject develops significant or serious adverse events causing discontinuation of study lens wear
- Subjects who have experienced a Corneal infiltrative Event (CIE) deemed by the investigator to be a serious adverse event.
- Investigator's clinical judgment regarding the subject safety
- Subject missed two consecutive study visits

For discontinued subjects, the Investigator will:

- Complete the current visit (scheduled or unscheduled)
- Complete the Final Evaluation, indicating the reason that the subject was discontinued from the study
- Record the spherocylindrical refraction with best corrected distance visual acuity
- Collect used test article(s) (worn or brought to the visit) from the subject and discard them, unless otherwise stated in Section 7.2
- Collect all unused test article(s) from the subject

An additional subject will be enrolled if a subject discontinues from the study prematurely.

In cases where a subject is lost to follow-up, every possible effort must be made to contact the subject and determine the reason for discontinuation/withdrawal. The measures taken to follow up must be documented including two written attempts and a certified letter (or equivalent) as the final attempt.

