14.5. Primary Analysis

Electronic LogMAR Visual Acuity will be analyzed on the analysis population using a linear mixed model. The model will include the experimental design factors: visit, test condition (AO1D/SCR), sequence of the test conditions as fixed effects. Subject will be included as a random effect. Age and gender will be included as fixed covariates when appropriate. The covariance between residual errors from the same subject across test conditions for the same test method will be selected based on the finite-sample corrected Akaike's Information Criterion³. Covariance structures considered may include: Homogenous compound symmetry (CS) and Unstructured covariance structure (UN). The structure that returns the lowest Akaike Information Criteria Corrected (AICC) will be selected as the structure that best fit the data.

Comparisons among the test conditions will be carried out using 95% confidence intervals constructed of pairwise least-square means (LSM) differences from the linear mixed model. Non-inferiority will be established if the upper confidence limit is less than 0.05. If non-inferiority is attained, superiority will be tested. Superiority will be concluded if upper confidence limit is less than 0.

In all models, the Kenward and Roger method (Kenward and Roger, 1997)⁴ will be used for the calculation of the denominator of degrees of freedom.

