14.6. Secondary Analysis – Quick Contrast Sensitivity

The area under the contrast sensitivity function curve will be analyzed on the analysis population using a linear mixed model. The model will include the experimental design factors: test method (qCSF), visit, test method by period interaction, test condition (AO1D/SCR), sequence of the test conditions, and test method by test condition interaction as fixed effects. Subject will be included as a random effect. Age and gender will be included as fixed covariates when appropriate. The covariance between residual errors from the same subject across test conditions for the same test method will be selected based on the finite-sample corrected Akaike's Information Criterion (Keselman et al. 1998)³. Covariance structures

considered may include: Homogenous compound symmetry (CS) and Unstructured covariance structure (UN). The structure that returns the lowest Akaike Information Criteria Corrected (AICC) will be selected as the structure that best fit the data.

Comparisons among the test conditions for each test method will be carried out using 95% confidence intervals constructed of pairwise least-square means (LSM) differences from the linear mixed model. Statistically significant difference will be established if the lower confidence limit is above 0 or the upper confidence limit is less than 0.

In all models, the Kenward and Roger method (Kenward and Roger, 1997)⁴ will be used for the calculation of the denominator of degrees of freedom.

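### The superiority step in section 14.5 would be concluded on the per-protocol set alone, and the ITT set defined in section 14.3 is used in no analysis

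*Combined protocol and SAP*

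**What the plan says.** Section 14.3 defines three sets and then ties the analysis to one of them: "The analysis population includes all per-protocol population subjects (see below". To be in the per-protocol set a subject must complete all visits and must be someone who "did not substantially deviate from the protocol as determined by the trial cohort review committee prior to database hard lock". Reasons for exclusion go into a memo to file.

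The ITT set is also defined there: "All randomized subjects regardless of actual treatment and subsequent withdrawal from study or deviation from protocol", with at least one recorded observation. Sections 14.5, 14.6, 14.7 and 14.9 do not use it.

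Section 14.5 fits the logMAR acuity model on the analysis population. Non-inferiority requires an upper limit below 0.05. The section continues: "If non-inferiority is attained, superiority will be tested". Superiority requires an upper limit below 0 from the same model on the same subjects.

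Section 14.6 uses the same set: "The area under the contrast sensitivity function curve will be analyzed on the analysis population using a linear mixed model".

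Section 5.2 describes masking of subjects and says that "the mask should not be broken until all subjects have completed the study and the database is finalized". It also advises the investigator not to disclose the assignment to site or sponsor personnel. It does not say whether the cohort review committee is masked.

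**The concern.** Per-protocol is a usual choice for a non-inferiority test, where off-protocol data can pull the two conditions together. That reason does not carry over to superiority. There the familiar safeguard is the randomised set, because exclusions made after randomisation can favour one condition. In 14.5 the question changes between one sentence and the next, but the population does not.

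Two features make selective exclusion possible. What counts as a substantial deviation is left to committee judgement. In addition, lens insertion, settling and fit assessment happen only under AO1D, so some deviations can arise only in that condition.

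The synopsis lists marketing claims among the study's post-marketing purposes, so a superiority statement for the lens could be put to use. If the plan is followed exactly, nothing in the analysis would show a reader whether exclusions produced or removed that statement.

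**Working it through.** **Tracing the sets.** The analysis population equals per-protocol (14.3). The acuity tests (14.5) and the contrast sensitivity test (14.6) are both run on it. Section 14.7 names no population, and 14.9 plans no imputation and no all-randomised analysis. ITT otherwise appears only in the abbreviation list.

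**The SD.** The plan gives no figure for this point, but its sample-size table supplies the scale. From 14.2: SD 0.08, intraclass correlation 0.5, margin 0.05. The paired-difference SD is 0.08 × √(2 × (1 − 0.5)) = 0.08. A paired non-inferiority t-test with this SD reproduces the plan's 24 and 63 eyes at 90% power, using one-sided alpha 0.05 (power 0.907 and 0.903). This supports reading 0.08 as the SD of the difference. The alpha used in that table is a separate matter.

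**Assumptions for the size of the effect.** One value per period; 42 completers (section 4.3); zero true difference over all 42; m completers excluded whose AO1D-SCR difference is x logMAR worse than that of the rest (a higher value is worse).

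**Formula.** If the retained mean is μ, then (42 − m)μ + m(μ + x) = 0, so μ = −m·x/42. With n = 42 − m, SE = 0.08/√n and df = n − 2, the chance that the upper limit falls below 0 is the noncentral t distribution function at −t(0.975, df) with noncentrality μ/SE.

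| m | x | retained mean | noncentrality | false superiority |
|---|---|---|---|---|
| 2 | +0.02 | −0.00095 | −0.075 | 3.0% |
| 4 | +0.02 | −0.0019 | −0.147 | 3.5% |
| 2 | +0.05 | −0.0024 | −0.188 | 3.8% |
| 4 | +0.05 | −0.0048 | −0.367 | 5.5% |
| 2 | −0.02 | +0.00095 | +0.075 | 2.1% |
| 4 | −0.05 | +0.0048 | +0.367 | 1.0% |
| 4 | 0 | 0 | 0 | 2.5% |

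At 0.02 logMAR per letter (14.2), the extreme shifts are 0.00095/0.02 = 0.05 letter and 0.0048/0.02 = 0.24 letter.

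**Other SDs, worse direction.** Averaging both eyes gives SD 0.08 × √((1 + r)/2), which is 0.057 at between-eye correlation r = 0 and 0.08 at r = 1. The lower end of the range (m = 2, x = 0.02) becomes 3.0% to 3.2%, and the upper end (m = 4, x = 0.05) becomes 5.5% to 7.3%. With SD 0.10 the two ends are 2.9% and 4.7%.

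**Multiplicity.** Section 14.4 plans a simulation-based adjustment, while 14.5 speaks of plain 95% intervals, so its reach is unclear. If it gave one-sided 1.25% for each of the two acuity conditions (an assumption), the two end cases in the worse direction become 1.5% and 3.0%, against a nominal 1.25%.

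**ITT on the same data.** In a simulation of 200,000 runs at SD 0.08, ITT gave 2.5% (m = 2, x = 0.02) and 2.3% (m = 4, x = 0.05). Per-protocol gave 3.0% and 5.4%.

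**Section 14.6.** No SD is given for the area under the log contrast sensitivity function. The same shifts in SD units are 0.02/0.08 = 0.25 and 0.05/0.08 = 0.625. They give a falsely declared two-sided difference in 5.1% and 6.5% of trials, against 5%.

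**The case against.** Superiority is peripheral. The only primary hypothesis in section 2.3 is non-inferiority, and the objectives and endpoints do not mention superiority. This stands, and it limits the weight of the point.

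The plan has safeguards: exclusions are decided before hard lock, justified in a memo, and made while the mask is meant to be intact. A reader might infer that the committee works unmasked, because the masking described is mainly of subjects. The documents do not support that. Section 5.2 also advises against revealing assignment to site and sponsor personnel, and the committee's membership and access are not stated. The safeguards lower the risk, but they do not show what the estimate would be without the exclusions.

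A reader might also infer that the rule inflates false superiority claims. That does not follow either. The direction of any bias is unknown, exclusion unrelated to outcome leaves the rate at 2.5%, and the upper case needs 4 of 42 completers (9.5%) excluded who average a full margin worse than the rest.

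Lens-fit failures look like the clearest treatment-dependent loss: "if lens fit is unacceptable subject will be discontinued from the study". They add little here. Steps 2.8 and 3.8 come before acuity testing, while section 8.2 tells the investigator, for discontinued subjects, to "Complete the current visit (scheduled or unscheduled". Whether AO1D acuity would exist for them is therefore unclear, and the passages should be reconciled. Even if it does exist, a subject with one period contributes little to the within-subject contrast in a 2x2 crossover.

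For 14.6, the hypothesis is that no statistical difference will be found. A falsely declared difference would work against that hypothesis, so the concern there is marginal.

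**Conclusion.** The point holds in a limited form. By the plan's own rule, superiority would be concluded on a set selected after randomisation, and the ITT set has no use. The non-inferiority analysis is not faulted. Under the stated assumptions (SD 0.08, 42 completers, 2 to 4 excluded, a difference of 0.02 to 0.05), false superiority runs from about 3.0% to 5.5% if the excluded subjects did worse on AO1D, and from about 2.1% to 1.0% if they did better, against 2.5%. These figures show scale and do not predict what will happen, because the documents give no exclusion rate and no direction. The stronger conclusion, that the trial's primary result is unreliable, is not supported. This is an optional, cheap improvement.

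**What to change.** In 14.3 and 14.5, keep per-protocol as the deciding set for non-inferiority. Run the same model on the ITT set as 14.3 already defines it, with all available data. Conclude superiority only if the ITT upper limit is also below 0. False superiority under this joint rule cannot exceed the ITT rate.

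In 14.6, report the same model on ITT as a sensitivity analysis only.

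Report exclusions from per-protocol by sequence and reason. The inputs are already collected: discontinuation reasons at the final evaluation (step F.1), deviations tracked under section 10, and the exclusion memo of 14.3. State also whether the cohort review committee is masked.

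The cost is one extra model run per endpoint and one table. A few off-protocol observations enter the ITT estimate, and the superiority rule becomes slightly stricter. The gain is mainly the return of completers excluded for deviations, who have both periods.
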